Double-Blind Treatment Period																												
Cohort	No. of Subjects	Dose Regimen																										
Cohort 1	22 subjects	200 mg KD025 QD (subjects will receive 1 KD025 200 mg and 1 matching placebo tablet in the morning and a matching placebo in the evening)																										
Cohort 2	22 subjects	200 mg KD025 BID (subjects will receive 1 KD025 200 mg and 1 matching placebo tablet in the morning and KD025 200 mg in the evening)																										
Cohort 3	22 subjects	400 mg KD025 QD (subjects will receive 2 KD025 200 mg tablets in the morning and a matching placebo in the evening)																										
Cohort 4	22 subjects	600 mg/day KD025 (subjects will receive 2 KD025 200 mg tablets in the morning and 1 KD025 200 mg tablet in the evening)																										
Cohort 5	22 subjects	Control (subjects will receive 2 matching placebo tablets in the morning and 1 matching placebo tablet in the evening)																										
32-Week Open-Label Continuation Period (Week 16 through Week 48)																												
All subjects		400 mg KD025 QD (subjects will receive 2 KD025 200 mg tablets in the morning)																										
Duration of Treatment	
Up to 48 weeks of treatment: All subjects will receive blinded study drug (either KD025 or placebo) from randomization, for a total of 16 weeks. Subjects randomized to KD025 or placebo will have the option to continue 400 mg of KD025 QD treatment for an additional 32 weeks in the open-label treatment period.
																											
Concomitant Treatment	
Subjects will be counseled to avoid non-prescribed medicines or complementary alternative medicines excluded by the study. Any medications a subject receives from signing ICF through the end-of-study (30-Day Follow-Up visit) will be documented.
 
Subjects may be receiving low-dose oral corticosteroids (<math>\leq 10</math> mg daily prednisone or equivalent) at study entry. Oral corticosteroid dose must be
																											

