**Table 1-1 Schedule of Assessments**

Assessments	Screening	Double-Blind Treatment Period					32-Week Open-Label Continuation Period						Unscheduled or Early Termination b Visit (±3 days)	30-Day Follow-Up c (±3 days)
		Week 1	Week 4	Week 8	Week 12	Week 16 a	Week 20	Week 24	Week 30	Week 36	Week 42	Week 48		
Visit	1	2	3	4	5	6	7	8	9	10	11	12		
Day	-28 to -1	1 (Baseline)	28 (±3 days)	56 (±3 days)	84 (±3 days)	112 (±3 days)	140 (±3 days)	168 (±3 days)	210 (±3 days)	252 (±3 days)	294 (±3 days)	336 (±3 days)		
Informed consent	X													
Demographics and Medical history	X													
Physical examination d	X	X				X		X		X		X	X	X
Vital signs e	X	X	X	X	X	X	X	X	X	X	X	X	X	X
Hematology and serum chemistry f	X g	X	X	X	X	X	X	X	X	X	X	X	X	X
Lipid panel h	X g	X				X	X	X		X		X	X	X
PT, PTT, INR	X g	X				X	X	X		X		X	X	X
TSH	X g	X				X	X	X		X		X	X	X
Urinalysis	X g	X	X	X	X	X	X	X	X	X	X	X	X	X
Supine 12-Lead ECG i	X	X				X						X	X	
Pregnancy test j	X	X	X	X	X	X	X	X	X	X	X	X	X	X
Randomization k		X												
Photographs (optional) l		X				X						X	X	X
Punch Biopsy (optional) m		X				X								
PD whole blood sample n		X		X		X						X	X	X

Assessments	Screening	Double-Blind Treatment Period					32-Week Open-Label Continuation Period						Unscheduled or Early Termination b Visit (±3 days)	30-Day Follow-Up c (±3 days)
		Week 1	Week 4	Week 8	Week 12	Week 16 a	Week 20	Week 24	Week 30	Week 36	Week 42	Week 48		
Visit	1	2	3	4	5	6	7	8	9	10	11	12		
Day	-28 to -1	1 (Baseline)	28 (±3 days)	56 (±3 days)	84 (±3 days)	112 (±3 days)	140 (±3 days)	168 (±3 days)	210 (±3 days)	252 (±3 days)	294 (±3 days)	336 (±3 days)		
PASI Scoring	X e	X	X	X	X	X		X		X		X	X	
PGA Scoring		X	X	X	X	X		X		X		X	X	
DLQI	X	X	X	X	X	X		X		X		X	X	
Study drug administration p		X		X		X						X		
Dispense/Collect study drug Diary q		X				X						X	X	
Concomitant medications		To be collected from the date that the informed consent form is signed until 30 days after last dose of study drug.												
Adverse events														

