2.2 Study Design

This is a Phase 2, double blind, randomized, placebo-controlled, dose-finding, safety, tolerability, and efficacy study.

This study will be performed in adult male and female subjects with moderate to severe chronic plaque psoriasis who are candidates for systemic therapy or phototherapy. Subjects who have signed an Institutional Review Boards/Independent Ethics Committees (IRBs/IECs) approved informed consent form (ICF) and have met all of the inclusion/exclusion criteria will be enrolled. Approximately 110 subjects will be randomly assigned to each of the 5 dose cohorts in a 1:1:1:1:1 manner to achieve 22 evaluable subjects at 16 weeks in each cohort.

Table 1: Cohorts

Cohort	Number of Subjects	Treatment
Cohort 1	~22	200 mg KD025 QD
Cohort 2	~22	200 mg KD025 BID
Cohort 3	~22	400 mg KD025 QD
Cohort 4	~22	600 mg/day KD025 (administered as 400 mg in the morning and 200 mg in the evening)
Cohort 5	~22	Matching placebo BID

Study drug will be orally administered in a double-blind fashion for an initial 16 weeks. All subjects will be given the option to receive KD025 400 mg QD for an additional 32-weeks in an open-label treatment period (week 16 through week 48).

For all subjects, including those who discontinue from the study prematurely, a Follow-Up visit will occur 30 days (\pm 3 days) after the last dose of study drug.

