3.1.2 General Considerations

General considerations for descriptive statistics and presentation for continuous and categorical data are given below.

Continuous data will be described using descriptive statistics: number of observations (n), mean, standard deviation, median, minimum and maximum. Frequencies and percentages will be used for summarizing discrete (categorical) data. When categorical data are presented, the percent will be suppressed when the count is zero in order to draw attention to the nonzero counts. The denominator for all percentages, unless otherwise specified, will be the number of subjects in the cohort or in the specified analysis population.

Means, medians, standard deviations, and confidence intervals (CI) will be reported to one decimal place more than the data reported on the CRF or by the vendor. Minimum and maximum will be reported to the same number of decimal places displayed on the CRF or by the vendor. P-values will be reported to 4 decimal places.

Efficacy analysis will be performed on blinded period and entire treatment duration. Safety analysis will be performed on blinded period, open-label period and entire treatment duration.

Unless otherwise indicated, all summary tables for blinded period and entire treatment duration will be presented by the following groups: cohort 1, cohort 2,

cohort 3, cohort 4, cohort 5, and all KD025. For open-label period, summary tables will be presented by the actual dose group (400 mg KD025 QD for all subjects).

Because of the exploratory nature of the study, no adjustments will be made for the multiplicity of endpoints.

Last Observation Carried Forward (LOCF) method will be incorporated when applicable.

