3.9.1 Adverse Events

AEs will be coded using the Medical Dictionary for Regulatory Activities (MedDRA) dictionary (Version 20.0 or higher). TEAEs for blinded period and entire treatment duration are any AEs occurring or worsening in severity after the first administration of study medication. TEAEs for open-label period are any AEs occurring or worsening in severity after Week 16. All AEs (including SAEs) will be graded using the 5-point CTCAE V5.0 scale (mild, moderate, severe, life threatening, or death); their causality with KD025 will be classified into following 5 classes: definitely related, probably related, possibly related, unlikely related, not related. The Investigator will further assess the relationship of adverse events to cGVHD or the underlying disease.

The number and percentage of patients who experienced at least one TEAE as well as the number and percentage of patients who experienced adverse events of each specific system organ class (SOC) and preferred term (PT) will be presented. For the presentation of AE incidences, the SOCs and the PTs within each SOC will be presented by decreasing total frequency. Tabulation by maximum severity and relationship to KD025 will also be included by treatment group.

TEAEs, Grade ≥ 3 TEAEs, SAEs and TEAEs leading to dose modification / discontinuation will be summarized according to treatment arm, system-organ-class, and preferred terms. These analyses will be repeated for events considered related (definitely related / probably related / possibly related) to KD025.

Subject listings will be provided for SAEs, AEs resulting in study drug discontinuation and deaths.

AEs will also be presented in listings. Time to onset and duration of AEs will be included in listings, along with action taken and outcome.

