3.9.2 Clinical Laboratory Evaluation

The summary statistics (including number, mean, standard deviation, median, minimum and maximum) of all laboratory variables and changes from baseline will be calculated for each visit or study assessment by treatment group. For parameters of WCC, neutrophils (absolute count), lymphocytes (absolute count), monocytes (absolute count), Hb, platelets, ALP, ALT, AST, GGT, total bilirubin, GFR, plots of mean / mean changes from baseline with the corresponding standard error will be displayed.

For shift tables, laboratory results will be classified using the CTCAE V5.0. All graded laboratory parameters will be summarized separately for hematology and biochemistry. Corresponding shift tables to compare baseline to the worst post-baseline grade within the treatment period will be provided.

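### Entire-duration safety percentages by randomised cohort depend on how many subjects chose to continue, and the SAP plans no measure per unit of time at risk

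*SAP*

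**What the plan says.** SAP 3.1.2 sets three reporting windows: "Safety analysis will be performed on blinded period, open-label period and entire treatment duration". Tables for the blinded period and the entire duration are laid out by randomised cohort, placebo included, plus a pooled KD025 column. Open-label tables are laid out by the dose actually taken.

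The windows differ in length. SAP 2.2 gives "Study drug will be orally administered in a double-blind fashion for an initial 16 weeks" and then "All subjects will be given the option to receive KD025 400 mg QD for an additional 32-weeks". The protocol synopsis puts the maximum at "Up to 48 weeks of treatment".

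The adverse event measure in SAP 3.9.1 is "The number and percentage of patients who experienced at least one TEAE", repeated by system organ class, preferred term, severity and relationship. For laboratory grades, SAP 3.9.2 says "Corresponding shift tables to compare baseline to the worst post-baseline grade within the treatment period will be provided". On denominators, SAP 3.1.2 says "The denominator for all percentages, unless otherwise specified, will be the number of subjects in the cohort or in the specified analysis population". SAP 3.9 puts all safety analyses on the safety population, and SAP 3.2 defines no open-label population.

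Exposure enters only as a descriptive summary of treatment duration (SAP 3.7), and time to onset only in listings (SAP 3.9.1). Protocol 12.8 adds counts of events per preferred term, but these are not divided by exposure. Neither document has a person-time rate or a time-to-first-event summary.

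**The concern.** The percentage of subjects with at least one event grows with time at risk, even when the underlying rate does not change. In the entire-duration tables, time at risk is partly set by each subject's own choice at Week 16, and that choice may differ by cohort. A cohort in which more subjects continued, for instance because they responded better, can look less safe simply because it was watched for longer.

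Early stopping adds to this. Protocol 8.2.1 and 9.4 contain stopping criteria tied to related events and liver tests, so time on treatment may differ by dose for a second reason.

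At stake is the reading of safety across doses in a dose-finding trial with about 22 subjects per cohort, if that reading is taken from the entire-duration tables or from setting blinded and open-label columns side by side.

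**Working it through.** **The plan's own safety figure.** SAP 3.12 gives the chance of seeing at least one event among 36 subjects. For a 6% rate, 1 − 0.94^36 = 0.892 (stated: about 90%). For 4%, 1 − 0.96^36 = 0.770 (stated: about 80%, so 3 points short). These rates carry no time unit. The point does not depend on them, but 6% is a useful starting value.

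**Inputs from the documents.** Windows of 16, 32 and 48 weeks (SAP 2.2; protocol synopsis). Scheduled post-baseline hematology and chemistry draws in Table 1-1: Weeks 4, 8, 12 and 16 (4 draws); then, under "32-Week Open-Label Continuation Period", Weeks 20, 24, 30, 36, 42 and 48 (6 draws); 10 in all. SAP 3.9 keeps unscheduled results out of summary tables, so scheduled draws drive the tabulated worst grade.

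**Assumptions not in the documents.** Constant hazard; 16-week incidence p of 6% or 20%; continuation share c of 40% or 80%. The 20% is a round figure. Protocol 4.3 reports liver enzyme elevations in about 20% of subjects in an earlier three-month study, so it is not fanciful.

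**Incidence by window.** Over w weeks, incidence = 1 − (1 − p)^(w/16).

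| p (16 weeks) | 32 weeks | 48 weeks |
|---|---|---|
| 6% | 1 − 0.94² = 11.6% | 1 − 0.94³ = 16.9% |
| 20% | 1 − 0.80² = 36.0% | 1 − 0.80³ = 48.8% |

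**Entire-duration percentage.** This is (1 − c) × p + c × (48-week incidence).

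- p = 6%, c = 40%: 0.6 × 0.060 + 0.4 × 0.1694 = 10.4%
- p = 6%, c = 80%: 0.2 × 0.060 + 0.8 × 0.1694 = 14.8%; difference 4.4 points
- p = 20%, c = 40%: 0.6 × 0.200 + 0.4 × 0.488 = 31.5%
- p = 20%, c = 80%: 0.2 × 0.200 + 0.8 × 0.488 = 43.0%; difference 11.5 points

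Over the full range of c from 0 to 100%, the figure runs from 6.0% to 16.9% at p = 6%, and from 20.0% to 48.8% at p = 20%.

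**Open-label percentage.** If the denominator is subjects who entered, it is 11.6% (p = 6%) or 36.0% (p = 20%), above the blinded figure. If it is all treated subjects, it is c times that. At c = 40% and p = 20%, 0.4 × 36.0% = 14.4%, below the blinded 20%. At c = 50% and p = 6%, 0.5 × 11.6% = 5.8%, below 6.0%. The two readings point in opposite directions.

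**Worst grade over k draws.** With probability q per draw and independent draws, 1 − (1 − q)^k gives, for k = 4, 6 and 10: 3.9%, 5.9% and 9.6% at q = 1%; 18.5%, 26.5% and 40.1% at q = 5%. Repeat values in one subject are likely to be correlated, which would make the rise smaller.

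**Does the remedy work?** At p = 6% the hazard is −ln(0.94)/16 per week, or 20.2 first events per 100 subject-years. In a simulation of 2,000,000 subjects, the crude percentages for 16 weeks, 48 weeks, 50% continuing and 90% continuing were 6.0%, 17.0%, 11.5% and 15.9%. The exposure-adjusted rates were 20.3, 20.2, 20.2 and 20.2. The artefact disappears when the hazard is constant.

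**The case against.** The best counter-argument is that the comparison that matters is already protected. The blinded period is reported separately, every arm there has the same planned 16 weeks and 4 draws, the SAP plans no safety test, and the protocol's primary safety endpoint is itself a percentage. Treatment duration is tabulated, and laboratory means and QTcF categories are shown by visit. All of this stands, and it limits the point to the entire-duration tables and to comparisons across periods.

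The sizes also rest on chosen inputs. At p = 6% the gap of 4.4 points is about one subject in 22 (0.044 × 22 = 1.0). At p = 20% it is about 2.5 subjects (0.115 × 22), less than one standard error of the difference between two cohorts (about 14.5 points). That is fair. But this is a shift built into the measure, added to chance variation, and a reader of the table cannot separate the two.

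Two stronger readings are tempting, and the documents do not support them:

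- *Open-label tables are bound to look more toxic than blinded ones.* The direction depends on the denominator. The default rules literally point to the whole safety population, on which the open-label figure can be the lower one. Subjects who stopped early for toxicity may also never enter, and the average rate of hematology and chemistry draws falls after Week 16 (every 4 weeks, then 6 draws in 32 weeks).
- *Lipid, coagulation and TSH results are distorted most, since they go from 1 post-baseline draw to 4.* SAP 3.9 and 3.9.2 tabulate grades for hematology and chemistry only. TSH, triglycerides, HDL and LDL have no grades in protocol Appendix A, and cholesterol is also in the chemistry panel (protocol Table 7-1), so it has 4 blinded-period draws. At most PT and PTT would fit.

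**Conclusion.** The point holds for the entire-duration tables. With identical event rates, cohorts whose continuation differs by 40 percentage points would differ by about 4 points (16-week incidence 6%) to 11.5 points (20%) by construction. These sizes assume a constant hazard and continuation of 40% versus 80%; the documents give no expected event rate by period and no continuation share, so they illustrate and do not forecast.

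Blinded and open-label percentages are also not directly comparable, because they cover 16 versus 32 weeks and 4 versus 6 scheduled hematology and chemistry draws. Which one would be higher cannot be said from the SAP. Between-cohort comparisons in the blinded period are not affected in this way; only unequal early discontinuation could disturb them.

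This is a cheap improvement to safety reporting. It does not put the trial's efficacy conclusions in question.

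**What to change.** In SAP 3.9.1 and Table 4:

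- Beside each crude percentage in the entire-duration and open-label tables of TEAEs, SAEs, Grade 3 or higher events and events leading to discontinuation, give subjects with a first event per 100 subject-years at risk, with a 95% CI. State when risk time starts and ends in each period.
- Use subjects who entered the open-label period as the open-label denominator.
- State that between-cohort safety comparisons rest on the 16-week blinded period.

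In SAP 3.9.2, show subject-years and the number of post-baseline draws with each hematology and chemistry worst-grade shift table.

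The cost is SAP wording, a few added table columns and a risk-time definition. Dose dates and event onset dates are already collected, so trial conduct does not change. There are two limits. The rates summarise risk well only if the hazard is roughly constant. Entire-duration rates will also still mix the randomised regimen with the open-label one, so in the placebo column they include time on open-label KD025; exposure adjustment does not cure that.

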3.9.2 Clinical Laboratory Evaluation

The summary statistics (including number, mean, standard deviation, median, minimum and maximum) of all laboratory variables and changes from baseline will be calculated for each visit or study assessment by treatment group. For parameters of WCC, neutrophils (absolute count), lymphocytes (absolute count), monocytes (absolute count), Hb, platelets, ALP, ALT, AST, GGT, total bilirubin, GFR, plots of mean / mean changes from baseline with the corresponding standard error will be displayed.

For shift tables, laboratory results will be classified using the CTCAE V5.0. All graded laboratory parameters will be summarized separately for hematology and biochemistry. Corresponding shift tables to compare baseline to the worst post-baseline grade within the treatment period will be provided.

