#### **4.3 Previous Clinical Experience with KD025**

A Phase 1 fed or fasted study (KD025-105) was conducted to evaluate the food effect as well as to further evaluate the safety and PK of a single 500-mg dose of KD025 administered orally to fed and fasted healthy males.

Study results showed approximately a 3-fold higher exposure (maximum serum concentration [ $C_{max}$ ] and area under the curve [AUC]) in the fed state compared with the fasted state. There were no treatment emergent adverse events (TEAEs) and no treatment-related AEs were reported in any subject after receiving KD025 in either the fed or fasted state. There were no clinically relevant changes in vital signs, physical examination (PE) findings, or electrocardiogram (ECG) parameters. There were no clinically relevant changes and no clinically meaningful trends in hematology, chemistry, and urinalysis laboratory results attributable to study drug during this study. Plasma concentrations achieved in this study were comparable to plasma levels achieved in previous studies at similar dose levels, where breakfast was provided immediately after dose administration. These studies support dosing KD025 with food.

KD025-205 was a Phase 2a, open-label study in 8 adult subjects with moderately severe psoriasis vulgaris who have failed first-line therapy. As with the other studies, 200 mg QD KD025 administered daily for 28 days was generally safe and well tolerated.

KD025-206 was a Phase 2a, open-label, dose-finding study in 36 adult subjects with moderately severe psoriasis vulgaris who have failed first-line therapy. The study was a 3-month, open-label study with 3 cohorts (200 mg BID, 400 mg QD, and 400 mg BID). KD025 was well tolerated in all subjects and demonstrated activity as measured by PASI. The only adverse experience was related to elevated alanine aminotransferase (ALT)/ aspartate aminotransferase (AST) levels in approximately 20% of the subjects. The KD025 400-mg BID group showed the highest (Grade 3) elevations. The 400-mg BID dose will not be pursued in future studies.

The Investigator's Brochure (IB) 2015 includes additional nonclinical and clinical information about this agent.

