Abnormalities in clinical laboratory tests that lead to a change in subject management (e.g., dose delay, discontinuation, requirement for additional medication or monitoring) are considered clinically significant for the purposes of this study, and will be recorded on the AE eCRF page. With the exception of LFTs, laboratory results will be classified using the Toxicity Grading Scale for Healthy Adult and Adolescent Volunteers Enrolled in Preventive Vaccine Clinical Studies (see Appendix A). Laboratory results for ALT, AST, alkaline phosphatase, GGT, and

bilirubin will be classified according to Table 9-2 in Section 9.4. If laboratory values constitute part of an event that meets criteria defining it as serious, the event (and associated laboratory values) must be reported as an SAE (see Section 11.3.1).

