## 9.4 Evaluation of Liver-Related Blood Tests

Clinically significant elevations of liver-related blood tests as defined below require immediate drug termination.

1. ALT or AST  $> 5 \times$ ULN
2. ALT or AST  $> 3 \times$ ULN and (total bilirubin  $> 2 \times$ ULN or INR  $> 1.5$ )
3. ALT or AST  $> 3 \times$ ULN with the appearance of fatigue, nausea, vomiting, right upper quadrant pain or tenderness, fever, rash, and/or eosinophilia ( $> 5\%$ )
4. If the total bilirubin is  $> 2 \times$ ULN then obtain direct bilirubin

If ALT or AST  $> 2.0 \times$ ULN, the subject should remain on study drug with **close observation** which includes:

1. Repeating liver enzyme, every 48 to 72 hours  
(Frequency of retesting can decrease to once a week or less if abnormalities stabilize or the study drug has been discontinued and the subject is asymptomatic.)
2. Obtaining a more detailed history of symptoms and prior or concurrent diseases

3. Obtaining a history of concomitant drug use (including nonprescription medications and herbal and dietary supplement preparations), alcohol use, recreational drug use, and special diets
4. Ruling out acute viral hepatitis types A, B, and C
5. Obtaining a history of exposure to environmental chemical agents

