3.9 Safety Analysis

Safety assessments include AEs, serious adverse events (SAEs), vital sign measurements, clinical laboratory evaluations (hematology and chemistry), and ECGs. Unscheduled visits for safety assessments will not be presented in summary tables, but will be presented in listings. All safety analyses will be performed using the safety population.

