3.14 Primary CSR Analysis

A primary CSR analysis will be conducted after conclusion of the study.

4 List of Tables, Figures and Listings

In all tables, figures and listing, results will be presented by treatment cohorts and overall, unless be otherwise specified.

Table 2: Demographics and Baseline Characteristics TLFs

T/F/L	Title	Population
T	Subject disposition	mITT
L	Subject disposition	mITT
L	Protocol deviations	mITT
T	Demographics and baseline characteristics	mITT
L	Demographics and baseline characteristics	mITT
T	Medical histories by primary system organ class and preferred terms	mITT
L	Medical history	mITT

Table 3: Efficacy TLFs

T/F/L	Title	Population
PASI		
T	The number (%) of subjects with a 75% decrease in PASI by Week 16	mITT
T	The number (%) of subjects with a 75% decrease in PASI by Week 48	mITT
T	PASI score, change and % change from baseline by visit	mITT
T	PASI change and % change from Week 16 to Week 48 visit	mITT
PGA		
T	The number (%) of subjects with “clear” and “almost clear” (excellent) in PGA at Week 16, 48	mITT
DLQI		

T/F/L	Title	Population
T	DLQI score, change and % change from baseline by visit	mITT
Exploratory Endpoints		
T	Descriptive statistics for IL-17 by visit	mITT

Table 4: Safety TLFs

T/F/L	Title	Population
T	Concomitant medications	mITT
L	Concomitant medications	mITT
T	Treatment exposure and compliance	mITT
L	Treatment exposure and compliance	mITT
T	Dose modifications and interruption	mITT
L	Dose modifications and interruption	mITT
T	Overall summary of TEAEs	Safety
T	TEAEs by Soc/PT	Safety
T	TEAEs by PT	Safety
T	TEAEs by severity and PT	Safety
T	Treatment related AEs by PT	Safety
T	Serious TEAEs by Soc/PT	Safety
T	Serious TEAEs by PT	Safety
T	Treatment related SAEs by PT	Safety
T	Grade 3-5 TEAEs by Soc/PT	Safety
T	Grade 3-5 TEAEs by PT	Safety
T	Treatment related grade 3-5 AEs by Soc/PT	Safety
L	AEs	Safety
L	AE Leading to treatment discontinuation	Safety
L	Death	Safety
T	Lab values and their change from baseline	Safety
F	Lab values by visit	Safety
T	Shifts in CTC grade from baseline to highest grade post-baseline of laboratory	Safety
L	Lab values with CTC grade ≥ 3	Safety

T	Vital signs and their change from baseline	Safety
L	Vital signs	Safety
T	ECG parameters and their change from baseline	Safety
F	ECG parameters by visit	Safety
T	Number and percentage of subjects with QTcF by visit a) absolute ranges and b) change from baseline	Safety
T	QTcF abnormalities	Safety
L	ECG values	Safety

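### The SAP plans no by-cohort count or listing of subjects who meet the protocol's Section 9.4 liver criteria

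*SAP*

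**What the plan says.** **Protocol.** Section 9.4 states: "Clinically significant elevations of liver-related blood tests as defined below require immediate drug termination". Three patterns follow:

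1. ALT or AST > 5 × ULN.
2. ALT or AST > 3 × ULN with total bilirubin > 2 × ULN or INR > 1.5.
3. ALT or AST > 3 × ULN with listed symptoms or eosinophilia above 5%.

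The fourth item in that list is an instruction to measure direct bilirubin. From ALT or AST > 2 × ULN the section asks for repeat enzymes every 48 to 72 hours, less often once values stabilise or the drug is stopped. For grading, Section 7.2.4 says of the liver tests that "bilirubin will be classified according to Table 9-2 in Section 9.4", and Section 11.1 agrees. Section 4.3 gives the reason for attention: in the earlier 36-subject dose-finding study about 20% had raised ALT/AST, and "The KD025 400-mg BID group showed the highest (Grade 3) elevations".

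**SAP.** Section 3.9 describes the laboratory part of safety as "clinical laboratory evaluations (hematology and chemistry") and puts unscheduled results in listings only. Section 3.9.2 plans summary statistics by visit, mean plots and shift tables: "Corresponding shift tables to compare baseline to the worst post-baseline grade within the treatment period will be provided". For these, "laboratory results will be classified using the CTCAE V5.0". The one laboratory listing in Table 4 is "Lab values with CTC grade ≥ 3". No output counts or lists subjects by the 9.4 criteria.

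**The concern.** A dose-finding trial with arms from 200 mg to 600 mg per day should be able to say how many subjects at each dose crossed its own liver thresholds. ALT/AST elevation is the one adverse finding the protocol reports from the earlier dose-finding study. The planned laboratory outputs take each analyte separately, so they cannot identify a criterion that depends on two results in one person. The SAP does treat another safety signal this way: Section 3.9.4 counts subjects in QTcF bands by group and visit. Liver has no equivalent. At stake is the clarity of the liver comparison across doses; the efficacy analysis is not affected.

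**Working it through.** The plan states no figure on this point, so the check sets the criteria against the outputs.

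**Step 1. Can separate tables identify the combined criterion?** Take two subjects, values in × ULN, graded by Table 9-2.

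| Case | Subject A (ALT, bilirubin) | Subject B (ALT, bilirubin) | ALT grades | Bilirubin grades | Meets criterion 2 |
|---|---|---|---|---|---|
| X | 4, 1.0 | 1, 2.2 | 2, 0 | 0, 2 | nobody |
| Y | 4, 2.2 | 1, 1.0 | 2, 0 | 2, 0 | Subject A |

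In both cases the ALT table counts one Grade 2 and one Grade 0, and so does the bilirubin table. The shift tables are identical, yet only case Y contains an event. This holds on any grading scale, because separate tables carry no link between analytes within a subject.

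**Step 2. Does the Grade 3 listing catch the combined criterion?** Inputs from Table 9-2: ALT/AST Grade 2 is > 2.5 to 5.0 × ULN; bilirubin Grade 2 is > 1.5 to 2.5 × ULN. Criterion 2 needs ALT or AST > 3 and bilirubin > 2.

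- ALT or AST > 3 to 5 with bilirubin > 2 to 2.5: both Grade 2, so outside a Grade 3 listing.
- ALT or AST > 5, or bilirubin > 2.5: at least one value is Grade 3 or 4 and is listed.

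Part of the criterion, not all of it, therefore falls below the cut. This mapping is on the protocol's scale. The SAP grades by CTCAE V5.0, whose bands are in neither document. There the same gap exists only if Grade 3 starts above 3 × ULN for ALT/AST and above 2 × ULN for bilirubin.

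**Step 3. Are retest values used?** In the double-blind period scheduled bloods are about 28 days apart (Table 1-1), while retests come every 48 to 72 hours. A peak can easily fall between visits. SAP 3.9 leaves unscheduled results out of summary tables, and the only laboratory listing in Table 4 starts at Grade 3. A combined event in the band of Step 2, seen only on retest, could miss every laboratory output in Table 4.

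**Step 4. INR.** It is collected, but SAP 3.9 does not name coagulation, and neither Table 9-2 nor Appendix A has an INR grade. Table 1-1 schedules no INR at Weeks 4, 8, 12, 30 or 42, although chemistry is drawn at each. Matching INR to ALT on the same sample date would fail at those visits unless an extra sample was taken.

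**Step 5. Size.** One of 22 subjects rising from an assumed 0.5 to 5 × ULN moves the cohort mean by (5 − 0.5)/22 = 0.20 × ULN, so mean plots are a weak detector. Applying the earlier study's 20% to 22 subjects gives 0.20 × 22 = 4.4 with some ALT/AST elevation per cohort. That is illustrative only: the 20% pools three regimens including 400 mg BID, a higher daily dose than any here, and the protocol reports no bilirubin or INR rises with it. The documents give no rate for the combined event.

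**The case against.** The strongest reply is that these events do reach a count by arm. Meeting 9.4 stops the drug, protocol 7.2.4 makes a laboratory abnormality that leads to discontinuation an adverse event record, and SAP 3.9.1 and protocol 12.8 summarise events leading to discontinuation by treatment group. A reader might infer that the events would never be counted by dose; the documents do not support that. What stands is narrower. The adverse event route depends on entry by the site, spreads events over preferred terms and does not say which criterion was met. SAP Table 4 also carries only a listing of such events, not the summary by arm that 3.9.1 describes.

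Three further replies have force:

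- On Table 9-2, Grade 3 for ALT or AST begins above 5 × ULN, which is criterion 1. If that scale were used, shift tables would count criterion 1 for each enzyme at scheduled visits. It would be wrong to say that none of the criteria is tabulated.
- SAP 3.9.2 covers all laboratory variables and gives medians and maxima by visit, so a high scheduled value would show as a cohort maximum. INR may be included; the SAP is ambiguous, and one cannot say it goes unanalysed. Even so, a mean or maximum is not a count above 1.5.
- Protocol Section 12 promises listings of all captured data, so a reader could link results by hand. That makes the events recoverable, but the listing set in SAP Table 4 does not carry the promise through.

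**Conclusion.** The point holds in this form: the SAP plans no count by cohort, and no listing, of subjects meeting the Section 9.4 criteria, and its single-analyte outputs cannot show joint rises in one subject. The co-occurrence and unscheduled-result gaps do not depend on the grading scale. The two-Grade-2 pattern does: it is shown for ALT/AST with bilirubin on Table 9-2, and is unproven for the CTCAE grading the SAP uses. It does not extend to INR, which has no grade in the protocol's tables. The number of subjects affected cannot be estimated from the documents. This is an inexpensive improvement to safety reporting, worth making because liver enzymes are the known signal in a dose-finding trial.

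**What to change.** Add to SAP 3.9.2 and Table 4 one table by cohort and period, giving the number (%) of subjects with any post-baseline value, scheduled or unscheduled, of:

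- ALT or AST > 3 × ULN, and > 5 × ULN;
- total bilirubin > 2 × ULN;
- INR > 1.5;
- ALT or AST > 3 × ULN together with bilirubin > 2 × ULN or INR > 1.5 within a prespecified date window, not restricted to the same sample date.

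State that this table is an exception to the SAP 3.9 rule on unscheduled visits.

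Add a listing of every subject who met any 9.4 criterion, not limited to Grade 3 or higher, showing symptoms and eosinophils so that criterion 3 can be read. Name coagulation among the laboratory panels in SAP 3.9. Reconcile the liver grading scale: Table 9-2 in protocol 7.2.4 and 11.1 against CTCAE V5.0 in SAP 3.9.2.

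The cost is a little programming on data already collected. The protocol's thresholds and patient care are unchanged.
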